9.2 Sample Size and Randomization

The primary hypothesis examines change in gait speed (during NPW and WWT conditions). Setting an alpha level of .05, power of .80 and a medium effect size of defined as $f=.25$, the necessary sample size for detecting an interaction between time of test (pre and post), trial type (W or WWT) and imagery condition (Imagined gait or AC) is $n = 34$. Thus, our study completion goal of $n = 48$ (58 enrolled; 48 completed) is sufficient to detect our effects of interest and account for the 18% attrition rate expected during the study period (as observed in our previous studies (64)).

To detect a BOLD signal change at the individual subject level (i.e. first-level time-series modeling using SPM) at $p < 0.001$, a percent signal change of 0.34% is required using a published method and estimate of noise at a magnet strength of 3.0 Tesla (65). Based on this estimate, to detect a difference in contrast values between groups (i.e. second level analyses using SPM) at $p < 0.001$ and a power of at least .80, where the mean of one group's signal change is 50% of the other, 16 subjects per group are required. Thus, our study completion goal of $n = 48$ (24 in each condition) is sufficient to detect a main effect of imagery condition (imagined gait vs. AC) and leave room for the detection of interactions

9.2.1. Treatment Assignment Procedures

Group assignment randomization will be generated by [name] using sequential study numbers so that the assistant who enrolls the participants will be blinded to randomization assignment of the next participant until assigned. [name] will not be involved with subject testing or interventions.

Given the nature of our interventions, double-blinding both subjects and testers will not be feasible. But we will include a number of methods (besides randomization) to reduce bias.

- Selection bias will be reduced by concealing treatment allocation until the subject is entered into trial.
- Primary outcome is an objective endpoint (gait speed) and not subjective mobility complaints.

- Motor imagery and visual imagery interventions will be done at non-overlapping times.
- Participants and study staff will be instructed not to disclose group assignment or details of interventions.

9.3 Interim analyses and Stopping Rules

No interim analysis is planned for this pilot intervention of 48 volunteers. Early study termination will occur in the event of any unanticipated serious adverse event determined to be possibly, probably or definitely related to study procedures, failure to recruit at least 50% of the projected number of subjects within 4 months, or failure to retain at least 75% of study subjects to the conclusion of the protocol

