Study Title

Motor Imagery: A Pilot Intervention for Improving Gait and Cognition in the Elderly

Objectives:

Primary. Compared to a visual imagery intervention group, participants who are enrolled in the motor imagery intervention (MI) group will demonstrate:

P1: Significant improvements in gait speed during actual Walking and Walking While Talking

Secondary. Compared to a visual imagery intervention group, participants who are enrolled in the motor imagery intervention (MI) group will show:

P 2.1: Significant improvements in cognitive performance during Talking and Walking While Talking

P 2.2: Change in blood-oxygen-level dependent signal during Walking and Walking While Talking

Design and Outcomes

The investigators propose to conduct a single-blind randomized clinical trial to test the efficacy of a phone-based motor imagery intervention for improving gait and cognition in older adults between 65 and 85 years old

[figure not shown]

Figure 1. Participant Flow

Interventions and Duration

Participants will be randomized into either a 12-week phone-based motor imagery intervention or visual imagery intervention (active control condition). Both groups will complete 36 (15-minute) sessions (9 hours).

Participants will receive gait, mobility, cognitive and neuroimaging assessments at baseline and post-intervention (14-18 weeks after intervention). Baseline and post-intervention assessments will last about 3 hours over 1 day.

Sample Size and Population

We will enroll 48 cognitively-healthy older adults (24 in each group).

STUDY TEAM ROSTER

Principal Investigator:

[name]
Einstein College of Medicine,
[name]
[contact]
[contact]

[contact]

Main responsibilities/Key roles: She will coordinate efforts between team members, supervise implementation of study measures and supervise data collection. She will develop data analysis plans as well as scientific presentations and manuscripts based on the research findings.

Mentor:

[name]
Albert Einstein College of Medicine,
[name]
[contact]
[contact]

[contact]

Main responsibilities/Key roles: He will be responsible for the oversight of [name] responsibilities and for establishing benchmarks to ensure successful completion of this intervention. He will also be involved in developing data analysis plans as well as scientific presentations and manuscripts based on the research findings.

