3 STUDY DESIGN

Design: We propose a single-blind study of cognitively-healthy older adults randomized to a phone-based motor imagery or visual imagery (active control) intervention for 12 weeks (36 sessions)

Outcomes: The primary outcome is post-intervention change in gait speed during actual walking and walking while talking.

Secondary and tertiary outcomes include improvements in cognitive performance during Talking and Walking While Talking, changes in blood-oxygen-level dependent signal during Walking and Walking While Talking, improvement in executive function, and other mobility-related cognitive processes (speed of processing, memory and spatial navigation), and improved gait variability and other quantitative gait parameters during walking and walking while talking (see Clinicaltrials.gov-NCT02762604 for a comprehensive list).

Study population: 48 Bronx and Westchester county residents between 65 and 85 years old will be randomized into a phone-based motor imagery or visual imagery (control) intervention for 12 weeks (36 sessions)

Study location: Pre and post-intervention visits will be held at the Albert Einstein College of Medicine.

Approximate duration of enrollment period and follow-up: Potential recruits who meet eligibility criteria on the telephone are invited to baseline assessment and then randomized to motor imagery or visual imagery intervention. Baseline study assessments are limited to 180 minutes over 1 day to avoid fatigue. Telephone assessments are 15 minutes. Post-intervention assessments will be conducted within 4 weeks of the completion of the intervention.

We plan to enroll and randomize 48 participants over 36 months (1-2 per month). If necessary, we will ask for a no cost extension to allow for additional time to process and analyze the data, write manuscripts, and possibly apply for a follow-up grant.

Randomization and Blinding: We will include a number of methods to reduce bias.

- Selection bias will be reduced by concealing treatment allocation until the participant is entered into trial.
- Primary outcome is an objective endpoint (gait speed) and not subjective mobility complaints.
- Motor imagery and visual imagery interventions will be administered individually, and at non-overlapping times.
- Participants and study staff will be instructed not to disclose group assignment or details of interventions.

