5.4 Adherence Assessment

Sustaining adherence represents a major challenge in any RCT involving older adults. The phone-based delivery of the RCT improves likelihood of adherence. We have also incorporated multiple methods to promote adherence and reduce possibility of missing data.

- A permanent staff contact will be provided for each participant in the motor imagery and visual imagery intervention groups.
- Transportation and snacks will be provided on pre and post intervention assessment days.
- All participants will be compensated for attending in-house or telephone sessions (\$50 for the baseline visit, \$25 for the phone-based intervention, and \$50 for the post-intervention visit, for a total of \$125 for the study).

We propose to over-enroll by 20% to account for any attrition. Methods to account for non-compliance and missing data:

- Protocol violations. Subjects who miss 6 sessions due to any reason will be excluded from main analyses. We will explore dose response by adjusting number of sessions attended as a

covariate.

- We will identify 2 contact persons who do not live with the participant for when participant cannot be reached.
- Flexible scheduling with makeup sessions on alternate days.
- For each in-house study visit, we will allow a four-week window for completion.
- If the participant is acutely ill, is in the hospital, or has a temporary condition that interferes with walking (e.g. ankle sprain), we will attempt to complete the assessment at another time.
- Outcome adjudication. The research team will adjudicate events such as mobility disability in subjects who drop out based on medical interviews, contact interviews, and home assessments as required.

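### The recruitment stopping rule (half the projected subjects within 4 months) would terminate a trial that recruits exactly to its own 36-month plan

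*Combined protocol and SAP*

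**What the plan says.** Section 9.3 lists three triggers for ending the study: a related, unanticipated serious adverse event; a recruitment shortfall; and poor retention. The sentence is worded as mandatory: "Early study termination will occur in the event of any unanticipated serious adverse event" and so on through the list. The recruitment trigger is "failure to recruit at least 50% of the projected number of subjects within 4 months". Section 8 repeats it in the same terms. Neither section attaches a review step or any discretion to it.

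The accrual plan is in Section 3: "We plan to enroll and randomize 48 participants over 36 months (1-2 per month".

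The documents give two candidates for the projected number:

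- **48.** The Précis says "We will enroll 48 cognitively-healthy older adults (24 in each group", and Section 9.3 itself opens with "No interim analysis is planned for this pilot intervention of 48 volunteers".
- **58.** Section 9.2 has "58 enrolled; 48 completed", and Section 5.4 says "We propose to over-enroll by 20% to account for any attrition" (1.2 × 48 = 57.6, so about 58).

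The term is not defined, nor is the start of the 4-month clock. No section gives a month-4 target or a faster early accrual phase.

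**The concern.** The rule asks for half the sample in 4 of 36 months, which is 11% of the recruitment period. Section 3 describes no front-loading that could make this possible.

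A mandatory threshold that the plan itself cannot meet has two outcomes. Either a trial performing as designed is stopped at month 4, or the rule is set aside. Setting it aside departs from the protocol and leaves no usable numeric recruitment criterion for the DSMB, which Section 10.3.3 charges with evaluating recruitment, accrual and retention. It also weakens the safety and retention triggers, which stand in the same sentence.

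**Working it through.** **Inputs**

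- Recruitment period 36 months, rate 1 to 2 per month, N = 48 (Section 3)
- Alternative N = 58 enrolled (Section 9.2)
- Threshold 50% by month 4 (Sections 8 and 9.3)

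**Step 1. Reproduce the plan's own rate.** N / 36 gives 48 / 36 = 1.33 per month and 58 / 36 = 1.61 per month. Both lie within the stated 1 to 2, so Section 3 is internally consistent for either total.

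**Step 2. Compare month-4 accrual with the threshold.** Accrual by month 4 is 4 × rate. The threshold is 0.5 × N, and the time to reach it is 0.5 × N / rate.

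| N | Threshold | Rate per month | Accrued by month 4 | % of N | Month threshold is reached |
|---|---|---|---|---|---|
| 48 | 24 | 1 | 4 | 8% | 24 |
| 48 | 24 | 1.33 | 5.3 | 11% | 18 |
| 48 | 24 | 2 | 8 | 17% | 12 |
| 58 | 29 | 1 | 4 | 7% | 29 |
| 58 | 29 | 1.61 | 6.4 | 11% | 18 |
| 58 | 29 | 2 | 8 | 14% | 14.5 |

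The shortfall at month 4 is 16 to 20 participants for N = 48 (24 − 8 and 24 − 4) and 21 to 25 for N = 58 (29 − 8 and 29 − 4).

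**Step 3. Rate the rule requires.** For N = 48, 24 / 4 = 6.0 per month. That is 6.0 / 1.33 = 4.5 times the planned average and 3 times the top of the range. For N = 58, 29 / 4 = 7.25 per month.

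**Step 4. Allow for chance.** The documents give no accrual model, so Poisson accrual is an assumption here. P(at least 24 by month 4) is 9.9e-12 at 1 per month, 2.8e-9 at 1.33 and 3.7e-6 at 2. P(at least 29) is 6.7e-11 at 1.61 per month and 8.0e-9 at 2. The exact values matter little. Random variation does not rescue the rule.

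**Step 5. The milder reading.** Suppose the rule means half of the number projected by month 4, with the trial stopped if accrual falls below half of its own expectation. Under the same assumption, the chance of stopping an on-plan trial is:

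- 1 per month (mean 4, half is 2): P(X ≤ 1) = 9%
- 48 / 36 per month (mean 5.33, half is 2.67): P(X ≤ 2) = 10%
- 58 / 36 per month (mean 6.44, half is 3.22): P(X ≤ 3) = 12%
- 2 per month (mean 8, half is 4): P(X ≤ 3) = 4%

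**The case against.** **The contradiction depends on how one phrase is read.** If the projected number means the number projected by month 4, the threshold is about 3 (2 to 4 across the planned rates), and a trial with exactly the expected accrual passes. That is a possible reading, but the text does not support it. No section gives a month-4 projection. Section 9.3 names 48 volunteers in the sentence just before the rule, and the retention trigger in the same sentence is measured over the whole study. Even if this reading was intended, the rule needs rewording, because a mandatory threshold that could be 3, 24 or 29 cannot be applied.

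**Recruiting may not be the same as enrolling.** Section 6.2.2 dates enrolment at randomisation, and elsewhere the protocol speaks of potential recruits before that point. This is a fair point of wording, but no separate recruitment projection exists to which the rule could apply.

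**Recruitment oversight does not rest on this clause alone.** This stands. Section 10.3.3 gives the DSMB a general duty to evaluate accrual and to recommend continuation or termination, and Section 10.3.5 provides for biannual meetings and cumulative accrual reports. What would be lost is a workable numeric criterion. Those provisions do not override the mandatory wording.

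**The clause is administrative.** It does not touch the primary analysis, randomisation, type I error or power. That is true, but it decides whether the trial continues.

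**Conclusion.** The concern holds. On the plain reading, the recruitment trigger in Sections 8 and 9.3 contradicts the accrual plan in Section 3. The plan delivers 4 to 8 participants by month 4 where the rule demands 24 or 29, and a trial on schedule reaches half its total at month 18. The result is the same for both totals and every planned rate, and it needs no distributional assumption.

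It rests on taking the projected number as the trial total. The documents do not define the term, so the intended figure cannot be recovered from them. Under the alternative reading the rule would be passable, but would still stop an on-plan trial about 4% to 12% of the time if accrual is Poisson. Because termination is mandatory as written, the rule must be corrected.

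**What to change.** Reconcile Sections 3, 8 and 9.3 and replace the recruitment trigger in both places with one that:

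1. defines the projected number, as 48 or 58 and as the total or the number projected to date;
2. states when the clock starts;
3. sets the threshold against the Section 3 accrual curve.

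One example is DSMB review at month 12 if fewer than half of the participants projected to that date have been randomised. At 48 / 36 per month the projection is 16 and the threshold is 8. Under Poisson accrual an on-plan trial would be flagged with probability P(X ≤ 7 | mean 16) = 1.0%. If 58 is the enrolment target, the projection is 12 × 58 / 36 = 19.3 and half of it is 9.7, so the total must be settled first. The month, the fraction and the choice of review over automatic termination are for the sponsor to decide.

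The cost is one sentence in two sections, with no effect on endpoints or analysis. The downside is that slow recruitment is acted on later than month 4.

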9.4 Data Analyses

9.4.1 Primary outcome.

To examine gait speed during W and WWT we will use repeated-measures analyses that include time of test (pre and post), and trial type (W or WWT) as within subjects factors, and imagery condition (imagined gait or AC) as the between-subjects factor. Consideration of these analyses will focus on the three-way interaction between time of test, trial type, and imagery condition.

9.4.2 Secondary and tertiary outcomes.

Similar repeated-measures analyses will be used for our secondary outcomes measures/additional EF measures: Trail Making Test, the Letter Number Sequencing Test, the Stroop Color and Word Test, and the Flanker Interference Task. These measures include the time to complete Trails B corrected for Trails A from the Trail Making Test (Trails B-A), the raw score from the letter-number sequencing task WAIS-III, the raw response time to Color-Word (incongruent) trials corrected for Color (congruent) trials from the Stroop Color and Word Test (i.e., Stroop Interference) and the flanker interference response time measure (incongruent-congruent trials) from the Flankers interference task. Although three of these four measures are difference scores, our analyses will be completed on raw scores in order to maximize power. More specifically, for these measures we will use repeated-measures analyses that included time of test (pre and post) and trial type as within subjects factors, and imagery condition (imagined gait or AC) as the between-subjects factor. Trial type for the Trail Making Test will be Trails A and Trails B. Trial Type for the Stroop Color and Word Test will be congruent trials and incongruent trials. Finally, trial type for the Flanker task will be congruous and incongruous trials. Consideration of these analyses will focus on the three-way interaction between time of test, trial type, and condition. Analyses will focus on the primary outcome variables during training and to the end of training period.

All behavioral analyses will be corrected for multiple comparisons using the Bonferroni correction.

We will use a whole-brain multivariate Ordinal Trend Covariance Analysis (OrT-CVA) to analyze the BOLD signal during imagined walking and walking while talking (66, 67). This is because we are interested in determining how the use of the entire locomotion and executive

function systems change as a function of our imagined gait versus the active control condition. This is also because changes in neural activation are often masked by between-subject variability, an issue that is particularly important to consider in aging populations (68, 69). Our multivariate analyses will be performed with software developed by my co-mentor in advanced neuroimaging analysis, [name]: http://www.nitrc.org/projects/gcva_pca. OrT-CVA will be used to identify covariance patterns in the fMRI signal as a function of trial type (iT, iW and iWWT) at each study visit (pre and post-intervention) for each imagery condition (imagined gait or AC). OrT-CVA is similar to other covariance analyses such as partial least squares (70, 71) in that it employs a principal components analysis (PCA) to the data matrix that is then transformed to a matrix of the experimental design. Linear regression is then applied to detect a covariance pattern, or ordinal trend, in the fMRI signal as a function of task conditions that is based on a linear combination of a small set of principal components. An ordinal trend is a monotonic change in pattern expression as a function of task conditions, in this case as a function of trial type (iW, iT and iWWT). The expression of an ordinal trend is quantified in terms of a participant-specific expression score that is derived by projecting the covariance pattern onto a participant's scan for each task condition. These participant-specific (or pattern) expression scores can also be used for further analysis (e.g. to correlate with actual WWT performance). Note that the proposed multivariate analyses of fMRI data involve data reduction and therefore does not involve multiple comparisons.

Age, sex and education will be covariates in all analyses. Given that is a pilot RCT on a fairly small sample of participants, it is not statistically feasible to control for more than the basic covariates listed above. Additional variables/potential covariates will be recorded and carefully examined for potential inclusion as covariates or outcome measures in upcoming full-scale RCT, including stride length (cm), double support time (s), cadence (steps/min), swing time (s), stance time, stride length variability (SD), swing time variability (SD), the Geriatric Depression Scale (54), Medical Illnesses and Medication questionnaires (26, 55), Cognitive and Physical leisure activity questionnaire (56-58), Falls (59), Smoking and alcohol consumption questionnaires, Obesity (assessed with weight, waist circumference, and BMI (kg/m²)), Vision (Snellen's chart), Disability (7 ADLs using the scale developed by Gill and colleagues (60, 61), IADL (62, 63), Blood pressure (Sitting/Standing), Gray Matter Volume/Atrophy (T1-Weighted structural images) White Matter Integrity (Diffusion Tensor Imaging; DTI) and White Matter Hyper intensities (Fluid-Attenuated Inversion Recovery; FLAIR).

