1 STUDY OBJECTIVES

1.1 Primary Objective

Compared to a visual imagery intervention group, the participants who are enrolled in the motor imagery intervention group will demonstrate significant improvements in gait speed (cm/s) during actual Walking and Walking While Talking using an instrumented walkway (GAITRite® electronic walkway system).

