2.1 Study Rationale

Motor imagery involves envisioning motor actions without actual execution, and has been successfully used by athletes to improve athletic performance for quite some time; for reviews see

(9-12). There is some evidence that *motor imagery* can be used to improve gait, gait-related and cognitive functions in Parkinson's disease (13-15) and post stroke (16-20), but the rehabilitative potential of motor imagery in relatively healthy elderly is currently unknown.

Recent research suggests that gait engages a distributed network of brain regions including motor, basal ganglia, cerebellar and supplementary motor regions. Based on recent findings by us (21) and others (22, 23), we hypothesize that imagined gait can be used as a rehabilitative tool for improving gait in the elderly because it engages and strengthens similar neural systems as actual gait. Age-related gait decline is particularly evident in dual-task situations that demand Executive Functions (EF) and engage the prefrontal cortex (24-31). We recently developed and validated an imagined gait protocol against an actual gait protocol that involves an ecologically-valid dual-task situation (walking while talking; WWT) that predicts falls, frailty, disability and mortality in the elderly (21, 31, 32). This imagined gait protocol involves: 1) imagined Walking (iW), imagined Talking (iT) and imagined Walking While Talking (iWWT), 2) is associated with actual WWT performance, and 3) permits us to examine the underlying neural systems of gait with functional magnetic resonance imaging (fMRI). We have identified a pattern of brain regions whose activation change as a function of imagery task difficulty (iW < iT < iWWT), and is associated with actual WWT performance (21). Increases were most notably observed in cerebellar, precuneus, supplementary motor and prefrontal cortex regions. These initial findings suggest that our imagined gait protocol engages similar neural systems as actual gait and EF and command the development of this protocol into a tool for improving gait and EF in the elderly.

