The first aim of this research is to establish the efficacy of this imagined gait protocol to improve gait and EF in the elderly. We propose a pilot Randomized Clinical Trial (RCT) of 48 cognitively-healthy elderly adults who will be randomly assigned to an imagined gait intervention or an Active Control (AC; non-mobility related visual imagery) condition. The imagined gait (or AC) protocol will be administered during each study visit, and over the phone three times a week for three months (15 min/session, total of 36 sessions). Each participant will complete two study visits (pre and post). Pre-post intervention changes in gait velocity (cm/s) and cognitive performance (percent of correct letters provided; (correct/error x correct) x 100) during actual W, T and WWT will be our primary outcome measures. Age, Sex and Education will be covariates in all analyses. Other variables/covariates will be recorded (e.g. medical illnesses and history of falls), and carefully examined for potential inclusion as covariates in upcoming full-scale RCT.

The second aim is to determine neuroplasticity changes in response to our imagined gait intervention. To this end, participants will complete the imagined gait protocol (iW, iT and iWWT) during fMRI scanning at the pre and post-intervention study visits. We predict that our imagined gait protocol engages neural systems linked to actual gait and EF, while the AC condition engages neural systems linked to visual processing and imagery in general. We further predict that the neural systems engaged during our imagined gait protocol are strengthened following our imagined gait intervention.

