9 STATISTICAL CONSIDERATIONS

9.1 General Design Issues

Our goal in this preliminary single-blind RCT is to determine the efficacy of motor imagery for improving gait and cognition in older adults. Baseline distribution of covariates will be compared to assess adequacy of randomization to produce comparable groups of participants using appropriate graphical procedures and summary statistics.

9.1.1. *Primary outcome*

Gait speed was recommended to FDA as the preferred outcome for RCTs (39) because of its good validity, reliability, sensitivity to change, and predictive validity for multiple adverse outcomes.(39) We have reported that gait speed highly correlates with mobility related activities in our community.(40)

Reliability: We have reported excellent test-retest reliability of gait speed on GAITRite (Kappa >0.9).(41) Gait speed correlates highly with complaints of mobility limitations, falls and dementia in our studies.(41, 42)

Practice effects: Gait speed improved only by <2% when tested twice 8 weeks apart in controls in our pilot study suggesting that longer intervals between gait assessments may help minimize practice effects.

Walking while talking test (WWT) is a novel ecologically valid mobility measure developed by our group.(43, 44) Our studies establish the incremental validity of WWT speed over NPW speed for predicting adverse outcomes such as falls, frailty and disability.(44) Other investigators have shown that training older adults on WWT like tasks translates into clinically relevant outcomes such as reduced falls, better balance, or improved function.(45) Hence, establishing the efficacy of motor imagery on our co-primary outcome of WWT speed alone could be of high clinical impact and relevance (irrespective of its effect on NPW speed).

Reliability: We reported good inter-rater reliability ($r = 0.602$) on a previous WWT version.(43) In 31 EAS subjects, we had excellent test-retest ($r = 0.935$) and inter-rater reliability ($r = 0.918$) for WWT speed.

9.1.2. Secondary and Tertiary outcomes.

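### The primary analysis and the sample size rest on the three-way interaction, which asks whether the motor imagery effect differs between W and WWT, not whether motor imagery improves either speed

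*Combined protocol and SAP*

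**What the plan says.** The aim is stated in terms of each speed. Section 1.1 says that motor imagery participants, compared with visual imagery, "will demonstrate significant improvements in gait speed (cm/s) during actual Walking and Walking While Talking". The Précis says the same, and Section 3 adds: "The primary outcome is post-intervention change in gait speed during actual walking and walking while talking". Section 9.2 opens by tying the primary hypothesis to change in speed under both conditions. Section 9.1.1 treats the two speeds as separable: "establishing the efficacy of motor imagery on our co-primary outcome of WWT speed alone could be of high clinical impact", whatever happens to normal-pace walking.

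The analysis in Section 9.4.1 is a repeated-measures model with time (pre, post) and trial type (W, WWT) within subjects and imagery condition between subjects. Its stated emphasis is: "Consideration of these analyses will focus on the three-way interaction between time of test, trial type, and imagery condition". Section 9.2 gives n = 34 for an interaction of those three factors at alpha .05, power .80 and f = .25, with a completion goal of 48. No section gives the group-by-time term, or a group comparison within W or within WWT, a deciding role.

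The Study Rationale also lists cognitive performance beside gait velocity: both "during actual W, T and WWT will be our primary outcome measures". The Précis and Sections 1.2 and 3 make cognition secondary.

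**The concern.** A test of whether two effects differ is not a test of whether either exists. The objective would count an equal speed gain in both walking conditions as a full success, yet the named term has expectation zero in that case. Conversely, the term can be significant when one speed rises and the other falls, so a significant result shows benefit only once the cell means are read. Section 2.1 (Background) says the results may support a full-scale trial. A shared benefit could therefore be reported as a null primary result, or a difference between conditions reported as efficacy.

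The number of primary tests is also open. The plan gives cognition two different ranks, and the Bonferroni sentence in Section 9.4.2 does not say how many tests it covers.

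**Working it through.** **1. What the term estimates.** Let D_W and D_WWT be the group differences (motor minus visual imagery) in pre-to-post change, in cm/s. With two levels of each factor, the three-way interaction is D_WWT − D_W. If D_W = D_WWT it is zero at any sample size or correlation.

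**2. The plan's n = 34.** Inputs from Section 9.2: f = .25, alpha .05, power .80, two equal groups. The number of repeated measures and their correlation r are not stated. For two measures, use a noncentral F with df 1 and N − 2 and λ = 2f²N/(1 − r). Assuming r = .5, λ = .25N. N = 33 gives power .795 and N = 34 gives .807, so 34 reproduces. Setting λ = N·d²/4 gives d = √(8f²/(1 − r)), where d is the group difference in SDs of the analysed difference score. Here d = √(8 × .0625/.5) = 1.0. With four measures and r = .5 the same method gives 24. So 34 matches a two-group comparison of one difference score per person.

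**3. Power of the interaction at 48 completers.** Assumptions: equal SDs of W and WWT change; correlation c between the two changes; f = .25 taken as the full WWT gain, so d_WWT = 1.00, 1.29, 2.24 and 2.77 at r = .5, .7, .9 and .935. The last r is the WWT test-retest value in Section 9.1.1, whose interval is not stated. The interaction has d = (d_WWT − d_W)/√(2(1 − c)). For example, with r = .5, c = .5 and a W gain three quarters of WWT, d = .25/√1 = .25, λ = 48 × .0625/4 = .75 and power is .136.

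| Gain pattern | r | Interaction at .05, c = 0 / .5 / .8 | WWT alone at .025 |
|---|---|---|---|
| Equal in cm/s | any | 5 / 5 / 5% | 87% at r = .5 |
| W three quarters of WWT | .5 | 9 / 14 / 27% | 87% |
| same | .7 | 12 / 20 / 41% | 98% |
| same | .9 | 27 / 48 / 85% | >99% |
| same | .935 | 38 / 65 / 96% | >99% |
| W half of WWT | .5 | 22 / 40 / 76% | 87% |
| same | .9 | 77 / 97 / >99% | >99% |
| WWT only | .5 | 67 / 92 / >99% | 87% |

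If both gains are 1.0 SD but the WWT change SD is k = 1.25 times that of W, d = (k − 1)/√(1 + k² − 2ck) and power is 8 / 12 / 20%.

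**4. Simulation check.** With 1.0 SD gains in both conditions, 24 per arm, c = .5 and 20,000 runs, the three-way term rejected in 4.96% of runs and group-by-time in 97.5%.

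**5. Significance without overall benefit.** With +0.5 SD in WWT, −0.5 SD in W and c = .5, d = 1.0 and the interaction has 92% power, although the average effect is zero.

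**The case against.** The strongest reply is that to focus on a term is not to let it decide. The same model estimates group-by-time and every cell mean, and a significant interaction read with those means can show a WWT benefit. That is true, and it is why the loss is stated conditionally. But the plan gives no other term an alpha, a decision rule or a sample-size basis, and Sections 9.2 and 9.4.1 name the same interaction independently.

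There is also a scientific rationale: "Age-related gait decline is particularly evident in dual-task situations that demand Executive Functions (EF". It supports testing dual-task specificity, and the interaction does well when only WWT improves. No stated objective, however, requires the WWT gain to exceed the W gain.

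The low percentages depend partly on treating f = .25 as the whole single-speed gain. Section 9.2 applies it to the interaction, and on that basis 48 completers give 92% at r = .5. This stands as a limit on the unequal-gain rows. Holding f at .25 also means a gain of one full between-person SD of gait speed at every r, which no section supports with an SD or a cm/s figure. Neither point affects the equal-cm/s case, except that a Bonferroni correction would push its rejection rate below 5%.

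Finally, the same two-measure calculation applied to one speed also gives 34 at .05 (42 at .025), so the target of 48 completers need not rise on the plan's own assumptions. That is correct: the fault is in what is tested more than in the number.

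**Conclusion.** The concern holds. The stated primary focus and the stated basis for the sample size test dual-task specificity, while the objective is improvement in each speed. For gains equal in cm/s the loss is total, and this follows from algebra without any assumption. For similar but unequal gains it is large at low correlations (9% to 27% against 87% at r = .5, W gain three quarters of WWT). It is small or absent at high r and c, or when only WWT improves. The unequal-gain figures rest on assumed r, c and effect size, none of which the plan supports with data. This should be fixed before analysis: as written, the test could miss a benefit that the objective counts as success.

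**What to change.** In Section 9.4.1, name as primary the group difference in change for W and for WWT separately (or ANCOVA on post-intervention speed adjusted for that condition's baseline), adjusted for age, sex and education. Make the three-way interaction a secondary test of dual-task specificity.

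State the co-primary rule, which is the sponsor's choice:
- **Either speed suffices:** alpha .025 each. This fits Section 9.1.1.
- **Both required:** alpha .05 each. This is a possible reading of Section 1.1.

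In simulation with 1.0 SD gains in both speeds and 48 completers (40,000 runs, c = 0 / .5 / .8), power is 98 / 96 / 93% for either and 86 / 87 / 89% for both.

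Group-by-time averaged over W and WWT is an alternative already in the model that needs no alpha split. At 48 completers it has 95% to >99% power for 1.0 SD gains in both speeds, but only 43% to 67% if WWT alone gains 1.0 SD (c from .8 to 0).

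Reconcile the rank of cognitive performance between the Study Rationale and the Précis and Sections 1.2 and 3, and state how many tests the Bonferroni correction covers. Restate Section 9.2 for the chosen tests with r and effect size given, and report whatever power results. It should also settle enrolment. The Précis says "We will enroll 48 cognitively-healthy older adults (24 in each group", while Section 9.2 has 58 enrolled to yield 48. If 48 are enrolled and 18% are lost, 48 × .82 = 39.4, or about 39 completers. Per-speed power at .025 is then:

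| Difference in change | 48 completers | 39 completers |
|---|---|---|
| 1.0 SD | 87% | 78% |
| 0.5 SD | 29% | 23% |

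**Cost.** Wording only; no new data. Alpha is split under the either-speed rule. If benefit is confined to WWT and c is about .5 or more, the interaction would have had more power (92% or more against 87%). If cognitive measures stay primary, for example four tests at .0125, per-speed power at 1.0 SD falls to 80% with 48 completers and 69% with 39.
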